Data for this research study will be collected at two sites, the University of Oregon Prevention Science Institute in Portland, OR, and Loma Linda University in Loma Linda, CA. Approximately 1/3 of the sample will be recruited and assessed by the UO site. The UO site will be responsible for all data management and ~~but will not receive any~~ some protected health information (PHI) from the Loma Linda site in order to recruit participants for Cohort 5. For example, names, addresses, birthdays, and medical histories previously collected by Loma Linda research staff when potential participants were added to a waitlist ~~will not be shared with the Oregon site. The data sharing agreement between the two institutions has been modified to allow this sharing of information.~~

Methods for recruitment, baseline data collection, and parent groups will differ in this study between cohorts 1 and 2 due to the COVID-19 pandemic and the increased physical distancing required to limit spread of the virus. Cohort 1 began with in-person data collection in homes and in-person parent groups. Cohort 1 was in the middle of parent groups when the “stay at home” orders were issued; groups then shifted to a remote/ Zoom format, as did all subsequent data collection. In contrast, all phases of the research project (baseline data collection, parent groups, follow-up data collection) will be conducted remotely for Cohort 2 (and additional cohorts, if any). There is only one exception to this: if/ when it is deemed safe by the University/ State of Oregon for us to meet in person with preschoolers who are not wearing masks, we will conduct the ADOS and Stanford-Binet tests in person (these tests are part of the “lab visit” described below). If current restrictions are not lifted by the end of the study period, we will simply forgo collection of the ADOS and Stanford-Binet.

Because methods for recruitment, baseline data collection, parent groups, and immediate follow-up data collection differed between cohorts, descriptions of these methods are provided separately for each cohort. The methods described for lab visits, teacher data, and 6- and 12-month follow-up data collection apply to both cohorts and are labeled as such.

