Prior to the baseline assessment, parents will be randomly assigned by the Data Manager to either the behavioral parent training group with a mindfulness component (BPT-M) or an education component (BPT-E) by means of a random numbers table. An approximately equal distribution of families will be assigned to each of the two conditions. Families will be told of their condition assignment at the end of the observation task in the baseline visit.

Cohort 2

Recruitment methods are described below in section D. Interested parents will either contact the PRO-Parenting Project by phone or by completing a form on our project website. If the family indicates interest in participation, trained staff will conduct a phone screen (“Cohort 2 Script for initial contact phone screen” and “Cohort 2 script clinical screen baseline”). If the family meets eligibility for the study, they will be mailed an assessment packet, consent form, and return envelope, and will be scheduled for a series of 3 remote appointments for the purposes of baseline data collection (“Cohort 2 script for confirmation call to schedule remote home visit”). Information gathered from the initial screening calls will be destroyed for families who do not meet eligibility requirements, as well as for those who do meet requirements but choose not to participate. For families who proceed to the study, information gathered from the screening call will be used to assess parenting stress, which is a variable of interest to this study.

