Prior to the baseline assessment, parents will be randomly assigned by the Data Manager to either the behavioral parent training group with a mindfulness component (BPT-M) or an education component (BPT-E) by means of a random numbers table. An approximately equal distribution of families will be assigned to each of the two conditions. Families will be told of their condition assignment at the end of the observation task in the baseline visit.

Parent Groups

Cohort 1

For our first cohort, two parent groups were run concurrently and face-to-face at King School in Oregon City, OR (this facility is a former elementary school managed by the Clackamas ESD for HeadStart classes and early childhood special education classes) until the COVID-19 pandemic forced the CESD to close the building on March 12, 2020. Prior to the building closure, childcare was offered during all sessions and provided by staff who worked at the ESD, who had experience working with children with DD, and who were willing to work for our project as a paid second job. After the building closure, the two parent groups for Cohort 1 were run as virtual meetings through the Zoom platform, and no childcare was provided.

Cohort 2

For our second cohort (and any later cohorts), the two parent groups will be run 100% as virtual meetings through the Zoom platform and no childcare will be provided. All materials required for participation in parent groups will be mailed to parents prior to the first session.

Both Cohorts

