For the primary main effects efficacy evaluation, BPT-M versus BPT-E, we will specify LGMs. For our primary intervention efficacy hypotheses, child outcomes are considered distal because they are not the primary active agent of intervention. Any BPT intervention effects on children are hypothesized to operate through, and be transmitted through, more-proximal mechanisms of reduced parenting stress, and in turn, improved parenting (Forehand, Lafko, Parent, & Burt, 2014). For growth outcomes, a sequential set of models tests the latent variances and model fit comparing a random intercept only versus linear growth or quadratic growth models to determine the optimal pattern of change (Duncan, Duncan, & Stryker, 2006). For example, we will test the hypothesis that the BPT-M will show greater 1-year reductions in child behavior problems relative to the BPT-E condition. This effect is hypothesized to be mediated first by improvements in effective parenting behaviors. Intervention impact on growth in positive parenting skills, in turn, is hypothesized to be mediated by reductions in parenting stress, the target of the E-BPT intervention.

For tests of mediation, we will use approaches outlined for SEM and LGM (Cheong, MacKinnon, & Khoo, 2001; Judd, Kenny, & McClelland, 2001; Kraemer, Wilson, Fairburn, & Agras, 2002; MacKinnon & Luecken, 2008), including tests of indirect effects following recommendations using bootstrapped standard errors for the asymptotically distributed multiplicative indirect terms and estimated bias-corrected confidence intervals (MacKinnon, Fairchild, & Fritz, 2007; Preacher & Hayes, 2008).

D. Research Population & Recruitment Methods

1. Participant Population:

Between the Oregon and California sites, we anticipate screening 300 families to recruit 230 children with DD and their families (n=150 in CA; n=80 in OR). This would result in roughly 115 participants in each of the treatment conditions, which will provide adequate statistical power to minimally detect modest to medium effects in our primary analyses. These effect sizes are conservative based on past research.

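### No blocking or stratification by site or cohort is stated, and neither enters the efficacy model, although each Oregon cohort is delivered as two parent groups

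*Combined protocol and SAP*

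**What the plan says.** Section C, Recruitment and Baseline Data Collection, describes allocation once under Cohort 1 and again, in the same words, under Cohort 2. Before the baseline assessment the Data Manager assigns each parent to BPT-M or BPT-E "by means of a random numbers table. An approximately equal distribution of families will be assigned to each of the two conditions". Nothing is said about blocks, strata or minimisation.

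Under Parent Groups, the Oregon cohorts each have two groups. For Cohort 1, "two parent groups were run concurrently and face-to-face at King School in Oregon City, OR" until the building closed. For Cohort 2 and any later cohort, "the two parent groups will be run 100% as virtual meetings through the Zoom platform". The text does not say one group per arm in those words. It follows because the first six sessions differ between BPT-M and BPT-E.

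The opening of section C separates the cohorts by mode: "Cohort 1 began with in-person data collection in homes and in-person parent groups", then moved to Zoom partway through the groups, whereas Cohort 2 is remote throughout. Section D adds different recruitment routes.

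Section D.1 plans 230 families, 150 in California and 80 in Oregon: "This would result in roughly 115 participants in each of the treatment conditions".

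The Data Analysis section lists the confounders to be controlled: child diagnosis, IQ or intellectual disability status, gender, concurrent services and demographic variables. Site and cohort are not among them.

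**The concern.** In a group-delivered trial with two groups per cohort, the allocation split within a cohort sets the size of each group. Group size is part of what families receive: the education sessions use pair work and then whole-group discussion, and the behavioral parent training uses discussion, role-play and feedback. A group of 6 running beside a group of 14 is not the same setting.

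Cohort also carries delivery mode, mode of the baseline assessment, recruitment route and stage of the pandemic. If the arms hold unequal shares of the cohorts, part of any difference between cohorts enters the arm comparison. The same applies to site. Equal totals of about 115 per arm do not prevent this, and the listed covariates do not remove it.

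**Working it through.** **Inputs from the documents.** N = 230 (150 California, 80 Oregon), about 1:1 allocation, two groups per Oregon cohort, and at least a Cohort 5 in California (section C). **Not given:** families per cohort, the number of cohorts at each site, and California's grouping and allocation procedure. **Assumed:** 20 or 40 families per Oregon cohort, and independent 1:1 assignment. The second assumption is the case being tested, not something the plan states.

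**Plan's own figure.** 150 + 80 = 230, and 230 / 2 = 115 per arm. This reproduces. The power statement in D.1 is in words only and cannot be reproduced.

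**Split within one cohort.** With X ~ Binomial(n, 0.5), P(larger group ≥ r) = 2 × P(X ≥ r).

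| Families in cohort | 60/40 or worse | 2:1 or worse |
|---|---|---|
| 20 | 12:8 or worse: 0.503 | 14:6 or worse: 0.115 |
| 40 | 24:16 or worse: 0.268 | 27:13 or worse: 0.038 |

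**At least one such cohort among Oregon's 80 families.** P = 1 − (1 − p)^k.

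- Four cohorts of 20: 60/40 or worse, 1 − (1 − 0.503)^4 = 0.94; 2:1 or worse, 1 − (1 − 0.115)^4 = 0.39.
- Two cohorts of 40: 60/40 or worse, 1 − (1 − 0.268)^2 = 0.46; 2:1 or worse, 1 − (1 − 0.038)^2 = 0.075.

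The answer therefore depends heavily on cohort size.

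**Site mix between arms.** Oregon's share overall is 80 / 230 = 34.8%. Under unrestricted allocation the difference in Oregon share between arms has standard deviation of about √(0.348 × 0.652 × 4 / 230) = 0.063. A simulation of 400,000 allocations gives a median absolute difference of 4 percentage points and a 95th percentile of 12. The probability of 10 points or more is 11%, and of 15 points or more 1.7%.

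**Overall split and power.** The 95th percentile of the larger arm is 130, that is 130:100. Taking two-sided alpha 0.05 and a standardised difference of 0.37 (both assumed, with no clustering or dropout), power is 80.1% at 115:115 and 79.4% at 130:100.

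**Efficiency within a cohort.** Relative efficiency at arm shares q and 1 − q is 4q(1 − q): 0.96 at 60/40 and 0.89 at 2:1.

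**With stratified blocks of 4 and 6.** The arms in a site-cohort can differ only by the unfinished part of the last block, so by at most 6 / 2 = 3 families. In a cohort of 20 the difference must be even, so the worst split is 11:9.

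**The case against.** The strongest reply is that a random numbers table is a source of randomness, not an allocation scheme. It can produce a simple, blocked or complete-list allocation. The sentence on approximately equal distribution states an intent to balance and appears separately under each cohort, so near-equal numbers within each cohort is a natural reading. This stands. A reader might infer that the trial used simple randomisation, but the documents do not establish that. Every probability above is conditional on it. What remains is that no mechanism for balance is named.

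A reader might also infer that site imbalance between arms is likely. The figures do not support this: a 10-point difference in Oregon share has about an 11% chance. Nor is the trial's overall power in question, and unrestricted randomisation is unbiased. Within a cohort, delivery mode is not mixed with arm: both Cohort 1 groups met in person at the same time and both moved to Zoom. Mode can enter only through unequal shares of the cohorts in each arm.

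Finally, California supplies 150 of the 230 families under its own institution's protocols, which are not part of the document. Its allocation method and grouping are unknown, so the two-group argument is confined to Oregon. Multiplying the risk across a supposed number of site-cohorts for the whole trial would require a layout that the documents do not give.

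None of this answers the absence of site and cohort from the covariate list, which does not depend on how the table was used.

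**Conclusion.** The point holds in limited form. The plan neither states a restriction that balances the arms within site and cohort nor adjusts for those factors, although cohort determines the delivery groups and several conditions of the study. If allocation is unrestricted, a 60/40 or worse pair of groups in a given cohort has probability about 50% at 20 families and 27% at 40, and 14:6 or worse has probability 12% at 20. These figures rest on assumed cohort sizes and on unrestricted allocation. The two-groups-per-cohort premise is documented for Oregon only, and one group per arm is implied there rather than stated.

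The consequence is reduced comparability of delivery groups and possible chance confounding with cohort. It is not an invalid randomisation or a material loss of overall power. The change is worth making because it costs almost nothing.

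**What to change.** 1. **All cohorts, assigned or not.** In the Data Analysis section, add site and cohort, as site-by-cohort strata, to the covariates of the efficacy growth models. Define site explicitly (for example, by which institution's protocol governs the family), because Oregon staff also recruit California families for Cohort 5.
2. **Any cohort still to be assigned.** Replace the random numbers table with a computer-generated permuted-block list, stratified by site and cohort, with randomly varying block sizes (for example 4 and 6). The Data Manager holds the list. Change the allocation paragraph under both cohort headings. Editing the Oregon text alone would not govern California families in Cohort 5, so make the matching change in the California protocol.
3. **Cohorts already assigned.** They cannot be re-randomised. Report the allocation method actually used, including any blocking, and the numbers assigned to each arm by site and cohort.

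**Cost.** One list, a few sentences in two protocols, and a few model degrees of freedom. If both sites ran five cohorts (an assumption), that is at most 2 × 5 − 1 = 9 indicators for each growth factor they predict. Blocking adds slight predictability, which varying block sizes limit. It balances the numbers assigned, not the numbers who go on to attend.

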The BPT-M group and the BPT-E groups will be led by staff with a minimum of a Masters-level education in clinical or counseling psychology or social work. These individuals will be trained and supervised by a doctoral-level licensed psychologist. Parents randomly assigned to the BPT-M group will receive six sessions of Mindfulness-Based Stress Reduction followed by the 10-week BPT intervention described below. The MBSR component of the BPT-M intervention will include six weekly 2-hour group sessions and 30-45 minutes of daily home practice guided by instructional audio CDs and an MBSR parent workbook (see “Baer Mindfulness Home Practice Log” for sample homework for the Mindfulness group). Formal mindfulness exercises aim to increase the capacity for mindfulness (present moment awareness with a compassionate, nonjudgmental stance) and include a body scan, mindful yoga, and sitting meditation. In the sessions, participants practice formal mindfulness exercises and ask questions relating to the practice of mindfulness in everyday life, and the instructor provides didactic instruction on stress physiology and using mindfulness for coping with stress in daily life.

Parents randomly assigned to the BPT-E group will receive six sessions of education about children with developmental delays. The BPT-E group will also consist of 6-weekly 2-hour education sessions where families will gain information regarding their child's development, disability, and associated considerations. Each week has a general topic for discussion. Topics include Preparing for Individualized Education Plan (IEP) meetings, Navigating regional service agencies, communicating with Teachers, Advocacy, Sibling Issues, and Community Resources. At the start of each session, group leaders provide some didactic material on the topic. Parents then break up into pairs for small group discussion (via “breakout rooms” when groups conducted via Zoom) followed by a larger group discussion and questions. Parents in this group will also receive homework each week (see “BPT-E Hand Out Session 2”). Following the 6-week educational intervention, families will receive the same 10-week Behavioral Parent Training intervention described below.

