Six months and twelve months after the groups have finished, there will also be phone appointments and virtual home visits to collect the 6-month and 12-month follow-up assessments. At these assessments, the parents will again be mailed the same packet of questionnaires used at prior waves of data collection and asked to complete it prior to the virtual home visit. They will again participate in a 45-minute phone or Zoom appointment and a 30-minute virtual home visit in order to complete the 3 play activities. In addition, a link to a Qualtrics survey regarding the impact of the covid-19 pandemic on their family will be sent to parents at the same time as the 6- and 12-month follow-up survey packets (See 'Impact of covid-19 survey for qualtrics_rev2').

"Lab Assessment"

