For Cohort 1, these data were initially collected via a phone interview lasting approximately 1 hour (see COVID-19 interview questions for PROParenting families_FINAL" and "COVID-19 survey questions for PROParenting families_4.14.20_Final") as a separate data collection activity in Spring 2020. Longitudinal data will be collected from this cohort via Qualtrics survey in Fall 2020 and at the time of 6-month and 12-month follow-up data collection as described above (see "impact of covid-19 survey for Qualtrics"). The Covid-19 survey collected at the 12-month follow-up will be slightly modified from the one given at earlier time points to have tighter time frames on questions (see "impact of Covid-19 survey for Qualtrics_rev2").

For Cohort 2, these data will be collected via Qualtrics survey at baseline and immediate follow-up data collection, as described above. At baseline, the completion of this Qualtrics survey will be facilitated by the family interventionist in an interview-format during the rapport building appointment; participants will complete it on their own at the time of immediate follow-up (see "impact of covid-19 survey for Qualtrics_rev2").

Data Analysis

Analyses will be conducted using standard normal theory regression and structural equation modeling (SEM) techniques, with a particular focus on latent growth modeling (LGM; Muthén & Curran, 1997). To isolate the added value of the MBSR component of the BPT-M intervention, primary intent-to-treat (ITT) efficacy hypotheses comparing the BPT-M with BPT-E will be specified within a set of sequential mediation analyses (DeGarmo, Patterson, & Forgatch, 2004). We will use CACE modeling (Jo, 2002; Little & Yau, 1998) for analyzing and adjusting effect sizes on the basis of participant compliance and dosage in both groups. CACE mixture models allow unbiased estimates of intervention contrasts by modeling unknown compliance status as missing data using the known compliance in the intervention of focus, thereby matching latent characteristics to the two group conditions. We will intentionally assess and control for potential confounding variables that pose a possible threat to the internal validity of the study, namely, child diagnosis (e.g., ASD), child IQ/intellectual disability status, child gender, concurrent child services, and demographic variables (e.g., ethnicity, family language, family structure, SES).

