Participation will be limited to parents of children ages 3 to 5 who are English-speaking. The rationale for the age restriction is that parents of children often exhibit heightened stress during the preschool years, while simultaneously experiencing a reduction in services because Early Intervention services in Oregon terminate when the child is 3 years of age. All parents must speak and understand English because the clinicians who will be delivering the intervention are all English speaking.

Inclusion Criteria:

- Having a child ages 3 to 5 years with an agency-identified DD in one or more functional areas who is receiving early intervention or early childhood/ preschool special education through an individualized family service plan (IFSP) or individualized education plan (IEP);
- Elevated parent-reported child behavior problems, as indicated by a T-score of 60 or above on the Total Problems scale of the child Behavior checklist;
- Elevated parenting stress, as indexed by a total score above the recommended cutoff at the 85th percentile on the Parenting Stress Index-4.
- Access to internet/ Zoom to complete online intervention and assessments during the study period.

Exclusion Criteria:

- Parents will be excluded if they screen positive for active psychosis, substance abuse, or suicidality through endorsement of screening questions for associated modules of the Structured Clinical Interview for DSM Disorders (SCID)-Research Version Non-Patient Edition;
- They are currently receiving any form of psychological or behavioral treatment at the time of referral (e.g., counseling, parent training, parent support group);
- The parent or child does not speak or understand English; or
- The child has sensory impairments (e.g., deafness, blindness,) or nonambulatory conditions that would necessitate the need for significant modifications to the lab and home visit protocols

Please note that lack of access to the internet/ Zoom is not an exclusionary criterion for this study. The PRO-Parenting Study is inviting every family who is interested to reach out to them. Our family interventionists will work with families to connect with community resources and existing supports to access the internet or acquire needed technology.

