The child is only involved in the assessment aspects of the study pre-intervention, post-intervention, and at follow-up. During these assessments the child is instructed to play on the floor with the parent for 20 minutes. This task requires the child to understand the researcher's directions, sit up on his or her own, explore different toys in the room, and interact with the parent. Therefore, if the child has a physical disability or sensory impairment that prevents him or her from participating in the play task, the family will be excluded from the study.

The sample will also include the teachers of each of the target children. "Teacher" will be defined as any professional that works directly with the child who would be able to report on behavior. If a child is not in school, this person may be a behavioral therapist or other service provider who works with the child. Babysitters who regularly care for the child and are able to accurately report on the child's behavior would also be allowed if there are no other options. A teacher will be identified at baseline, at the end of the intervention, and at 6 and 12 months post-treatment. These assessment points will span a total of 18 months, and children are likely to transition between teachers/ classrooms during this time frame. Thus, it is likely that different teachers will report on a given child's behavior across the span of the study. We anticipate that the final sample may include up to 500 teachers (150 in OR).

2. Recruitment Methods:

In order to reduce the burden on ESD staff during the COVID-19 pandemic, we altered our recruitment methods between Cohort 1 and Cohort 2. The two methods are described below and organized according to Cohort.

Cohort 1

Families at the Oregon site will be recruited through the Clackamas ESD. Families who meet the study criteria will be identified from this agency's computerized databases, and screened by agency staff. In order to protect

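### Child age is not a named covariate, although children enter across a two- to three-year age band and the mediation paths in Aims 2 and 3 are not protected by randomization

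*Combined protocol and SAP*

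**What the plan says.** All references are to the combined protocol and SAP.

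- **Entry age.** Section D.1 says "Participation will be limited to parents of children ages 3 to 5 who are English-speaking". The first inclusion criterion repeats the band: "Having a child ages 3 to 5 years with an agency-identified DD in one or more functional areas". Neither says whether the band stops at the fifth birthday or runs to the sixth.
- **Length of follow-up.** Section C, Parent Groups, gives the BPT-M arm "six sessions of Mindfulness-Based Stress Reduction followed by the 10-week BPT intervention"; the BPT-E arm has the same 6 plus 10 weeks. Follow-up visits come "Six months and twelve months after the groups have finished". Section D.1 says of the teacher assessments, which share these time points, "These assessment points will span a total of 18 months".
- **Measurement.** At the follow-up visits "the parents will again be mailed the same packet of questionnaires used at prior waves of data collection".
- **Covariates.** Section C, Data Analysis, undertakes to control possible threats to internal validity. It lists child diagnosis and then "child IQ/intellectual disability status, child gender, concurrent child services, and demographic variables". The demographic entry continues with examples (ethnicity, language, family make-up, socioeconomic status) and is open-ended. Child age does not appear.
- **Models.** The same section specifies latent growth models for the arm comparison and places the primary intent-to-treat hypotheses within sequential mediation analyses: intervention to stress, stress to parenting, parenting to child behavior.
- **Age and stress.** Section D.1 justifies the age limit by saying that parents' stress is often raised in the preschool years while services fall away.

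**The concern.** The list was written to name the child characteristics that could distort the results, and it includes four at child level. Age is the obvious fifth. The sample is heterogeneous in age by design, behavior problems at this stage may change at different rates in younger and older children, and the plan's own rationale treats the preschool years as a distinct period for parental stress.

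Two things are at stake, and they differ in weight.

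- **The arm contrast.** If age predicts rate of change and is left out, that variation stays in the error term and the contrast is less precise than it could be.
- **The mediation paths.** Families are randomized to an arm, not to a level of stress or parenting. If age drives change in stress and also change in behavior, part of the stress-parenting-behavior association is an age effect. The bootstrap and bias-corrected intervals planned for the indirect effects deal with sampling error and do not remove confounding.

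**Working it through.** **1. Span.** Treatment is 6 + 10 = 16 weeks, or 16/52.18 × 12 = 3.7 months. Post-treatment, 6-month and 12-month visits therefore fall at about 3.7, 9.7 and 15.7 months from the start of groups. The stated total is 18 months, which leaves room for scheduling around the groups. Hence about 16 to 18 months.

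**2. Age spread against follow-up.** The entry band is 24 months wide if it stops at 5.0 and 36 months if it runs to the sixth birthday. That is 24/15.7 = 1.5 to 36/15.7 = 2.3 times the follow-up. Children differ in age from each other by more than any one child ages in the study.

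**3. Share aged 6 or more at the last wave**, assuming entry ages uniform over the band (the documents give no distribution):

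| Reading of 3 to 5 | Formula | 15.7 months | 18 months |
|---|---|---|---|
| To the sixth birthday | t/36 | 44% | 50% |
| Stops at 5.0 | (t − 12)/24 | 15% | 25% |

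On either reading a sizeable share leaves the preschool years during follow-up, and entry age decides who.

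**4. Precision of the arm contrast.** The planned total of 230 cannot be rebuilt, because no alpha, power, effect size, SD or dropout is stated. The effect is therefore given as a percentage of variance. Assumed: waves at 0, 4, 10 and 16 months, slope SD 0.35 per month, residual SD 5, intercept SD 8.

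- Sum of squared deviations of the wave times from their mean of 7.5: 56.25 + 12.25 + 6.25 + 72.25 = 147.
- Variance of one child's estimated slope: 0.35² + 25/147 = 0.1225 + 0.1701 = 0.2926.
- Share that is true slope variation: 0.1225/0.2926 = 0.42.
- Proportion removed by adjusting for age: about 0.42 × r², where r is the correlation of age with true slope.

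| r | 0.42 × r² | Simulated variance ratio, with age / without |
|---|---|---|
| 0.2 | 1.7% | 0.99 |
| 0.3 | 3.8% | 0.96 |
| 0.4 | 6.7% | 0.94 |
| 0.5 | 10.5% | 0.90 |

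The simulation used N = 230 and 3,000 runs. The formula and the simulation agree to within about one percentage point. In families, the gain is 230 × (1/0.99 − 1) = 2 to 230 × (1/0.90 − 1) = 26.

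**5. Mediation paths.** The documents give no figures here, so this only illustrates scale. Take standardized variables within arm and suppose the mediator has no effect on the outcome, but age correlates a with mediator change and b with outcome change. Regressing outcome on mediator without age then gives a coefficient of a × b. With each at 0.2 this is 0.04; with each at 0.5 it is 0.25. The standard error of such a coefficient with 230 families is about 1/√230 = 0.066, so the spurious path runs from 0.04/0.066 = 0.6 to 0.25/0.066 = 3.8 standard errors. It multiplies straight into the indirect effect. The other listed covariates would remove some of this to the extent that they track age.

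**The case against.** **Age is not excluded.** The demographic entry is an open list of examples, and an analyst could well count child age as demographic. This stands: age is unnamed, not ruled out. But an unnamed covariate can be added or omitted after the data are seen.

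**The primary comparison is sound without it.** This also stands. Arms are randomized about 1:1, so age is balanced in expectation. At r = 0.2 the precision gain is about 1%, and the correlations and SDs above have no source in the documents.

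**The link between age and stress is thin.** The plan says stress is raised in the preschool years; it does not describe a gradient within ages 3 to 5. Concurrent services, one route from age to stress, is already a control. So confounding is plausible, not shown.

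**A stronger reading is tempting.** The entry criterion on child behavior is worded "as indicated by a T-score of 60 or above on the Total Problems scale of the child Behavior checklist". A reader might infer that the growth outcome is a T-score, and that scores drift as children outgrow the norms. The documents do not support this:

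- The T-score appears only as an entry threshold. Outcomes are parent report, teacher report and coded observation, with no metric stated.
- Neither the checklist form's age range nor the full contents of the mailed packet are given.
- The 1-year reductions in Data Analysis are a between-arm hypothesis.
- Even if scores were assumed to shift by 3 or 5 points in either direction at age 6, a simulation with 115 per arm and 4,000 runs kept the arm contrast unbiased (mean error at most 0.05 points, type I error 0.046 to 0.056). Its SD rose from about 1.05 to at most 1.10.

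Nor do the documents justify requiring raw scores, which carry ordinary maturation. An analysis of under-sixes could only be descriptive. If 44% are dropped, 115 × 0.56 = 64 per arm remain, and at an assumed two-sided 0.05 and 80% power the detectable difference rises from 2.80 × √(2/115) = 0.37 SD to 2.80 × √(2/64) = 0.50 SD.

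**Conclusion.** The point holds as an omission from the covariate specification. It does not show that the primary arm comparison is biased.

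- **For BPT-M versus BPT-E**, leaving age out costs about 1-10% of the variance of the slope contrast, conditional on an assumed age-slope correlation of 0.2-0.5 and the assumed SDs. Differential dropout by age could add to this; no dropout figure is given.
- **For Aims 2 and 3**, age is a plausible confounder of paths that randomization does not protect. The size of any bias cannot be derived from the documents. On the illustration above it ranges from well under one standard error to nearly four.

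The second reason carries more weight, because the plan builds its efficacy hypotheses into the mediation sequence.

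**What to change.** In section C, Data Analysis:

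1. Name child age at randomization in the list of control variables.
2. Enter it as a predictor of both the intercept and the slope in every child-behavior growth model.
3. Enter it as a covariate in the mediator and outcome equations of the mediation models, for both the stress-to-parenting and the parenting-to-behavior steps.

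It would also help to state in section D.1 whether the entry band ends at the fifth or the sixth birthday, since that decides how many children are 6 or older by the last visit.

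The cost is a few lines of text and a few extra parameters per model. No new data are needed: age is an entry criterion, so it is known for every child, and it is fixed before assignment, so adjusting for it cannot introduce post-treatment bias.
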